**Has been changed to:**

Maintenance Period

The day after the end of the Titration Period (Visit 5) and prior to or on the end date of the Maintenance Period (Visit 8) for subjects who complete the Maintenance Period, or the day after the end of the Titration Period (Visit 5) and prior to or on the date of the ETV for subjects who discontinue during the Maintenance Period. If a subject does not have a Visit 8/ETV, then either the date of the last scheduled or unscheduled visit during the Maintenance Period or the date of last known dose of study medication during the Maintenance Period, whichever is later, will define the end date of the Maintenance Period.

**Change #3**

**Section 3.5.3 Per Protocol Set**

The PPS includes all subjects in the FAS who did not have important protocol deviations.

**Has been changed to:**

The PPS includes all subjects in the FAS who did not have important protocol deviations considered to have an impact on efficacy as confirmed during a DEM conducted prior to study unblinding.

**Change #4**

**Section 3.7 Center pooling strategy**

It is planned to appropriately pool centers by geographic location. The final strategy for pooling will be determined at the DEM.

**Has been changed to:**

All centers will be pooled by country for the purpose of analysis.

**Change #5**

**Section 4.2.3 Definition of concomitant medication in case of missing dates**

With respect to definition of medication as concomitant, the following rule will be applied in case of completely missing stop and/or start date information:

Medications with a missing start date whose stop date is either unknown or after the date of the first dose of study medication will be considered as concomitant medication.

Medications with a missing start date whose stop date is prior to first intake of study medication will not be considered concomitant.

In subject data listings, dates will be displayed as reported.

**Has been changed to:**

With respect to definition of medication as concomitant, the following rule will be applied in case of completely missing stop and/or start date information:

Medications, excluding AEDs, with a missing start date whose stop date is either unknown or after the date of the first dose of study medication will be considered as concomitant medication.

AEDs with a missing start date whose stop date is unknown will be considered as lifetime AEDs. AEDs with a missing start date whose stop date is after the date of first dose of study medication will be considered concomitant.

Medications, including AEDs, with a missing start date whose stop date is prior to first intake of study medication will not be considered concomitant.

In subject data listings, dates will be displayed as reported.

**Change #6**

**Section 6.4.1 Number of Lifetime AEDs**

The number of lifetime AEDs defined as AEDs taken and stopped >28 days prior to Visit 1 (ie, prior to entry into the Baseline Period), will be summarized by treatment group and overall for the SS based on the following categorization: 1 to 3 AEDs, 4-6 AEDs, and  $\geq 7$  AEDs.

**Has been changed to:**

The number of lifetime AEDs defined as AEDs taken and stopped >28 days prior to Visit 1 (ie, prior to entry into the Baseline Period), or AEDs with a missing start date and unknown stop date, will be summarized by treatment group and overall for the SS based on the following categorization: 0 AEDs, 1 to 3 AEDs, 4-6 AEDs, and  $\geq 7$  AEDs.

#### **Change #7**

Added new Section 6.4.4, so subsequent sections have been renumbered.

#### **Section 6.4.4 Number of AEDs taken on day of first dose of study medication**

The number of AEDs taken on the day of first dose of study medication will be summarized by treatment group and overall for the SS based on the following categorization: 1 AED, 2 AEDs, and 3 AEDs.

#### **Change #8**

#### **Section 7 Measurements of treatment compliance**

##### Actual weight of study medication used

Actual weight of study medication will be determined for each visit. The weight used will be computed by comparing the weight of the bottles (including adaptors and caps) of oral solution at dispensation to their weight upon return.

Actual weight of study medication oral solution will be calculated at each visit using the following formula:

Actual weight of used oral solution (g) = Total weight of bottles (including adapters and caps) at Dispensation - Total weight of bottles (including adapters and caps) at Return

The actual weight used will also be determined for the Titration Period, Maintenance Period, and the entire Treatment Period (Titration+Maintenance Periods).

##### Expected weight of study medication used

Expected weight of study medication will be determined for each visit. The expected weight will be based on the actual number of days between visits, and the prescribed daily dosing of study medication oral solution.

The following formula will be used to calculate the expected weight of oral solution for the respective study medication dose:

Expected weight of used oral solution (g) = Daily prescribed oral solution (mL) x Number of days between visit x 1.1g/mL. Please note that the estimated weight of 1mL of LCM is 1.1g.

The expected weight will also be determined for the Titration Period, Maintenance Period, and the entire Treatment Period (Titration+Maintenance Periods).

##### Compliance

A subject's dosing compliance should be within 75-125% during each visit. Compliance to study medication dosing will be calculated for each visit, and will also be determined for the Titration Period, Maintenance Period, and the entire Treatment Period (Titration+Maintenance Periods).

For oral solution, compliance will be calculated using the following formula:

Compliance (%) = Actual weight of used oral solution (g) / Expected weight of used oral solution (g) x 100

For tablets, compliance will be calculated using the following formula:

Compliance (%) = (Number of tablets dispensed – Number of tablets returned) / (Number of tablets prescribed per day (2 tablets) x Number of days between visit)) x 100

**Has been changed to:**

The total weight of used oral solution (mg) will be calculated as:

(Sum of actual weight of used oral solution [g] / 1.1g/mL) x 10mg/mL

Note that the estimated weight of 1mL of oral solution is 1.1g, and the concentration is 10mg/mL.

Where:

Actual weight of used oral solution (g) = Total weight of bottles (including adaptors and caps) at Dispensation - Total weight of bottles (including adaptors and caps) at Return

The expected weight of used oral solution (mg) will be calculated as:

Sum of daily oral solution (mg) for each day in the corresponding time period

Where:

Daily oral solution (mg) = (Morning dose [mg/kg] + Evening dose [mg/kg]) x Baseline weight (kg)

Total amount of tablets (mg) will be calculated as:

(100 x [number of 100 mg tablets dispensed – number of 100 mg tablets returned] + 50 x [number of 50 mg tablets dispensed – number of 50 mg tablets returned])

Expected amount of tablets (mg) will be calculated as:

Sum of daily tablets (mg) for each day in the corresponding time period

Where:

Daily tablets (mg) = Morning dose (mg) + Evening dose (mg)

Compliance

Compliance during a time period will be calculated using data from the respective time period only as follows:

100 x (Total weight of used oral solution [mg] + Total amount of tablets used [mg]) / (expected weight of used oral solution [mg] + expected amount of tablets [mg])

A subject's dosing compliance should be within 75-125% during each visit. Compliance to study medication dosing will be calculated for each visit, and will also be determined for the Titration Period, Maintenance Period, and the entire Treatment Period (Titration+Maintenance Periods).

Compliance will be summarized separately for the Titration Period, Maintenance Period, and entire Treatment Period for the SS. It will be presented using descriptive statistics and additionally using the categorization <75%, ≥75% to ≤125%, and >125%.

---

## Change #9

### Section 8.1.1 Derivations of primary efficacy variable

The primary efficacy variable is the change in partial-onset seizure frequency per 28 days from Baseline to the Maintenance Period. Seizure frequency per 28 days will be based on the number of days for which seizure information was provided during the specified time interval.

Seizure frequency per 28 days will be calculated as ([number of seizures over the specified time interval] divided by [number of days in the interval]) multiplied by 28.

The partial-onset seizure frequency per 28 days will be calculated for both the Baseline Period and for the Maintenance Period, and the change from Baseline calculated.

#### Has been changed to:

The primary efficacy variable is the change in partial-onset seizure frequency per 28 days from Baseline to the Maintenance Period. Seizure frequency per 28 days will be based on the number of days for which seizure information was provided during the specified time interval.

Seizure frequency per 28 days will be calculated as ([number of seizures over the specified time interval] divided by [number of days in the interval]) multiplied by 28.

The partial-onset seizure frequency per 28 days will be calculated for both the Baseline Period and for the Maintenance Period, and the change from Baseline calculated.

If a seizure cluster is reported, the highest recorded daily seizure frequency during the Treatment Period for the seizure type associated with the report of a seizure cluster will be used as the imputed seizure frequency for the day on which the cluster occurred.

## Change #10

### Section 8.1.2 Primary analysis of the primary efficacy variable

Seizure frequency will be analyzed using analysis of covariance with terms for treatment and center (pooled appropriately), on log-transformed seizure frequency using the transformation of  $\ln(X+1)$ , where X is the seizure frequency. Log transformed Baseline seizure frequency will be used as a covariate. The seizure frequency between treatment and placebo will be compared using the least squares means (LSMs). The percent reduction over placebo will be estimated as  $100 \times (1 - \exp[\text{LSM}_{\text{LCM}} - \text{LSM}_{\text{placebo}}])$ . A 95% CI will also be calculated for the percent reduction over placebo.

Partial-onset seizure frequency per 28 days during the Baseline Period and during the Maintenance Period, and the change from Baseline will be summarized by treatment group. This summary will be repeated by treatment group and age group, using the levels defined in section 4.8.

#### Has been changed to:

Seizure frequency will be analyzed using analysis of covariance (ANCOVA) with terms for treatment and center (pooled appropriately), on log-transformed seizure frequency using the transformation of  $\ln(X+1)$ , where X is the seizure frequency. Log transformed Baseline seizure frequency will be used as a covariate. Assumptions for the parametric model will be evaluated by diagnostic (eg, Shapiro-Wilk test for normality) and graphical methods such as residual plots,

including normal probability plots, histograms, and plots of residuals versus Baseline covariate values and treatment. An assessment will be made with regards to the influence of individual observations (eg, extreme outliers) on the analysis. To the extent feasible, such potential influential observations will be identified prior to unblinding, and an assessment will be made with regard to the potential impact of such data, including the evaluation of alternative statistical methodology such as non-parametric methods. If deemed that a non-parametric method is warranted, an ANCOVA model on rank of seizure frequency per 28 days with terms for treatment and center (pooled appropriately) will be employed as the primary analysis. Ranked seizure frequency per 28 days during the Baseline Period will be used as a covariate.

The seizure frequency between treatment and placebo will be compared using the least squares means (LSMs). The percent reduction over placebo will be estimated as  $100 \times (1 - \exp[\text{LSM LCM} - \text{LSM placebo}])$ . A 95% CI will also be calculated for the percent reduction over placebo.

Partial-onset seizure frequency per 28 days during the Baseline Period and during the Maintenance Period, and the change from Baseline will be summarized by treatment group. This summary will be repeated by treatment group and age group, using the levels defined in section 4.8.

#### **Change #11**

##### **Section 8.3.3 PedsQL assessment**

The above algorithm will also be used to calculate an overall total scale score (all scales) for each subject.

Calculated values and change from Baseline for the total scale score and each of the 4 scale scores will be summarized for each visit and Last Visit by treatment group. Subgroup summaries by age will be performed using the age groupings for which different questionnaires were entered:  $\geq 2$  to  $\leq 4$  years,  $\geq 5$  to  $\leq 7$  years,  $\geq 8$  to  $\leq 12$  years, and  $\geq 13$  to  $\leq 18$  years.

##### **Has been changed to:**

The above algorithm will also be used to calculate an overall Total Scale Score (all scales) and the Psychosocial Health Summary Score (a combination of the emotional, social and school functioning questions) for each subject.

Calculated values and change from Baseline for the total scale score, psychosocial health score and each of the 4 scale scores will be summarized for each visit and Last Visit by treatment group. Subgroup summaries by age will be performed using the age groupings for which different questionnaires were entered:  $\geq 2$  to  $\leq 4$  years,  $\geq 5$  to  $\leq 7$  years,  $\geq 8$  to  $\leq 12$  years, and  $\geq 13$  to  $\leq 18$  years.

#### **Change #12**

##### **Section 9.1 Descriptive statistics of LCM and AED plasma concentrations**

The results of LCM and other AEDs plasma concentrations will be described by the method of descriptive statistics: arithmetic mean, SD, median, range, geometric mean, and geometric CV. The evaluations will be done based on separation by LCM maintenance dose level, and repeated by LCM maintenance dose level and age group.

##### **Has been changed to:**

The results of LCM and other AEDs plasma concentrations will be described by the method of descriptive statistics: arithmetic mean, SD, median, range, geometric mean, and geometric CV. The evaluations will be done based on separation by LCM maintenance dose level, and repeated by LCM maintenance dose level and age group.

Summarization of PK data relative to time after dose will be performed for the overall group and separated by AED therapy and possibly age groups.

### **Change #13**

#### **Section 9.2 Population pharmacokinetics**

Summarization of PK data relative to time after dose will be performed for the overall group and separated by AED therapy and possibly age groups.

A population PK modeling of the LCM concentration time data will be performed within the NONMEM software. The effects of age, body weight, AED therapy, and other covariates will be evaluated. Simulations will be undertaken for estimating dose adaptations leading to the same exposure as in adults.

The methods will be described in the Data Analysis Plan (DAP) and the results will be reported in a separate modeling report.

#### **Has been changed to:**

A population PK modeling of the LCM concentration time data will be performed within the NONMEM software. The effects of age, body weight, AED therapy, and other covariates will be evaluated. Simulations will be undertaken for estimating dose adaptations leading to the same exposure as in adults.

The methods will be described in the Data Analysis Plan (DAP) and the results will be reported in a separate modeling report.

### **Change #14**

#### **Section 10.1 Extent of exposure**

All the summaries described below will also be presented for the FAS.

The overall duration of study medication exposure during each of the Titration Period, Maintenance Period, entire Treatment Period, Transition Period, and Taper Period (defined in section 3.2.2) will be calculated, as follows:

Titration Period: date of last dose of study medication during the Titration Period minus the date of first dose of study medication plus 1.

Maintenance Period: date of last dose of study medication during the Maintenance Period minus the date of first dose of study medication during the Maintenance Period plus 1.

Entire Treatment Period: date of last dose of study medication during the entire Treatment Period minus the date of first dose of study medication plus 1.

Transition Period: date of last dose of study medication during the Transition Period minus the date of first dose of study medication during the Transition Period plus 1.

Taper Period: date of last dose of study medication during the Taper Period minus the date of first dose of study medication during the Taper Period plus 1.

Entire study: date of final dose of study medication minus the date of first dose of study medication plus 1.

The overall duration of study medication exposure will be summarized for each of the study periods defined above, and also for the entire study by treatment group, and repeated by treatment group and age group, and by treatment group and weight group using the levels defined in section 4.8.

In addition, the overall duration of study medication exposure will be summarized using the following categories for each of the study periods defined above, and also for the entire study by treatment group, and repeated by treatment group and age group, and by treatment group and weight group using the levels defined in section 4.8:

Titration Period:  $\leq 2$  weeks,  $>2-\leq 4$  weeks, and  $>4-\leq 6$  weeks.

Maintenance Period:  $\leq 2$  weeks,  $>2-\leq 4$  weeks,  $>4-\leq 6$  weeks,  $>6-\leq 8$  weeks, and  $>8-\leq 10$  weeks.

Entire Treatment Period:  $\leq 2$  weeks,  $>2-\leq 4$  weeks,  $>4-\leq 6$  weeks,  $>6-\leq 8$  weeks,  $>8-\leq 10$  weeks,  $>10-\leq 12$  weeks,  $>12-\leq 14$  weeks, and  $>14-\leq 16$  weeks.

Transition Period:  $\leq 2$  weeks, and  $>2-\leq 4$  weeks.

Taper Period:  $\leq 2$  weeks, and  $>2-\leq 4$  weeks.

Entire study:  $\leq 2$  weeks,  $>2-\leq 4$  weeks,  $>4-\leq 6$  weeks,  $>6-\leq 8$  weeks,  $>8-\leq 10$  weeks,  $>10-\leq 12$  weeks,  $>12-\leq 14$  weeks,  $>14-\leq 16$  weeks,  $>16-\leq 18$  weeks,  $>18-\leq 20$  weeks,  $>20-\leq 22$  weeks, and  $>22-\leq 24$  weeks.

**Has been changed to:**

The overall duration of study medication exposure during each of the Titration Period, Maintenance Period and entire Treatment Period (defined in section 3.2.2) will be calculated, as follows:

Titration Period: date of last dose of study medication during the Titration Period minus the date of first dose of study medication plus 1.

Maintenance Period: date of last dose of study medication during the Maintenance Period minus the date of first dose of study medication during the Maintenance Period plus 1.

Entire Treatment Period: date of last dose of study medication during the entire Treatment Period minus the date of first dose of study medication plus 1.

The overall duration of study medication exposure will be summarized for each of the study periods defined above by treatment group, and repeated by treatment group and age group, and by treatment group and weight group using the levels defined in section 4.8.

In addition, the overall duration of study medication exposure will be summarized using the following categories for each of the study periods defined above by treatment group, and repeated by treatment group and age group, and by treatment group and weight group using the levels defined in section 4.8:

Titration Period:  $\leq 2$  weeks,  $>2-\leq 4$  weeks, and  $>4-\leq 6$  weeks.

---

Maintenance Period:  $\leq 2$  weeks,  $>2-\leq 4$  weeks,  $>4-\leq 6$  weeks,  $>6-\leq 8$  weeks, and  $>8-\leq 10$  weeks.

Entire Treatment Period:  $\leq 2$  weeks,  $>2-\leq 4$  weeks,  $>4-\leq 6$  weeks,  $>6-\leq 8$  weeks,  $>8-\leq 10$  weeks,  $>10-\leq 12$  weeks,  $>12-\leq 14$  weeks, and  $>14-\leq 16$  weeks.

### **Change #15**

#### **Section 10.4.4.1 Complete neurological examination**

...

Summaries of shift from Baseline to Last Visit will be provided by treatment group based on categories normal, abnormal, not clinically significant, and abnormal, clinically significant. A listing of neurological examination findings from the complete neurological examination will also be provided.

#### **Has been changed to:**

...

Summaries of shift from Baseline to Last Visit will be provided by treatment group based on categories normal, abnormal, not clinically significant, and abnormal, clinically significant. A listing of abnormal neurological examination findings from the complete neurological examination will also be provided.

### **Change #16**

#### **Section 10.4.4.1 Brief neurological examination**

...

A listing of neurological examination findings from the brief neurological examination will also be provided. No summaries of the brief neurological examination findings are planned.

#### **Has been changed to:**

...

A listing of abnormal neurological examination findings from the brief neurological examination will also be provided. No summaries of the brief neurological examination findings are planned.

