Three double-blind, placebo-controlled, multicenter studies (SP667, SP754, and SP755) in 1308 adult subjects, aged 16 to 70 years, established the efficacy of oral LCM as adjunctive therapy (1 to 3 concomitant AEDs) in subjects with difficult to control partial-onset seizures. In these studies, LCM was initiated at a dose of 100mg/day (in 2 divided doses) and escalated to the randomized dose (LCM 200mg/day, LCM 400mg/day, or LCM 600mg/day) in LCM 100mg/day per week increments.

When oral LCM was administered as adjunctive therapy at doses up to LCM 600mg/day in the 3 double-blind, placebo-controlled, multicenter studies in subjects with partial-onset seizures, the most frequently reported treatment-emergent adverse events (TEAEs) were central nervous system- and gastrointestinal-associated events. A dose relationship was seen for the most frequently reported common TEAEs, including dizziness, nausea, and diplopia. The nature and frequency of AEs were comparable to adjunctive therapy with other marketed AEDs. Safety evaluations support the further development of LCM as an AED.

Pellock et al have recently conducted a systematic review of AEDs used in the treatment of partial-onset seizures (Bourgeois and Goodkin, 2012; Pellock et al, 2012). The AEDs that were shown to be superior to placebo for the adjunctive treatment of partial-onset seizures in adult clinical studies were also shown to be superior to placebo for adjunctive treatment of partial-onset seizures in the pediatric clinical studies (subjects >2 years of age) in which they were investigated. The efficacy and safety of LCM observed in clinical studies in adults and preclinical data, as well as many additional attributes of LCM, render the drug appropriate to investigate in pediatric subjects. These attributes include predictable and linear PK, lack of drug-drug interactions, easy twice-daily dosing, and the availability of 3 different types of formulations in multiple strengths (allowing for flexibility in dose range and individualizing treatment).

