11.9 Other safety measurements

11.9.1 Physical examination

Physical examinations will be performed according to the tabular schedules of study procedures (Section 5.2) by a medically qualified clinician licensed to perform the examination.

Subsequent to Visit 1, clinically significant physical examination findings should be reported as AEs.

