13.4.1 Safety analyses

Adverse events will be coded using the Medical Dictionary for Regulatory Activities (MedDRA®) and tabulated by System Organ Class (SOC) and preferred term (PT).

Treatment emergent AEs will be defined as those events which start on or after the date of first study medication administration and within 30 days following the date of last study medication administration, or whose severity worsens within this time frame. The incidence of TEAEs will be presented by SOC and PT. Serious AEs and TEAEs leading to withdrawal will also be tabulated and listed.

Other variables assessing safety are: ECG, measurements of laboratory parameters (hematology, clinical chemistry, urinalysis, and hormone status) and vital signs (including body weight, height and BMI), physical and neurological examination findings, assessments of Tanner stage (if applicable), Achenbach CBCL, and BRIEF-P/BRIEF.

Measurement and change from Baseline in continuous parameters (eg, vital signs and laboratory measurements) will be summarized using descriptive statistics. When analyzing categorical data (eg, overall assessment of 12-lead ECG) the number and percentage of subjects in each category will be presented by treatment group. In addition, shift tables may be used to evaluate the number and percentage of subjects having a different post-Baseline status when compared to their Baseline status. Laboratory, ECG, and vital signs data outside of the respective reference ranges will be listed and highlighted.

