### **3.9 Changes to protocol-defined analyses**

There are no changes to analyses specified in the protocol.

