### **10.4.4 Neurological examination**

#### **10.4.4.1 Complete neurological examination**

A complete neurological examination will be performed at Visit 1 (entry to study), Visit 2 (Baseline), Visit 8, and at ETV in case of early termination. A complete neurological examination will also be performed at Visit 4 of the Transition Period and at the Safety Follow-Up Visit.

The complete neurological examination will include selected assessment of: general neurological status (level of consciousness, mental status, speech), cranial nerves, reflexes, motor system (general motor status, muscle strength, muscle tone), coordination/cerebellar function, and sensation.

Summaries of shift from Baseline to Last Visit will be provided by treatment group based on categories normal, abnormal, not clinically significant, and abnormal, clinically significant. A listing of abnormal neurological examination findings from the complete neurological examination will also be provided.

Clinically significant neurological findings will be reported as AEs.

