#### **10.4.4.2 Brief neurological examination**

A brief neurological examination will be performed at Visit 3 to Visit 7. A brief neurological examination will also be performed at Visit 1 to Visit 3 of the Transition Period, and at Week 18, 19, or 20 of the Taper Period, as appropriate.

The brief neurological examination will include selected assessment of: general neurological status, reflexes, muscle strength, and coordination/cerebella function.

A listing of abnormal neurological examination findings from the brief neurological examination will also be provided. No summaries of the brief neurological examination findings are planned.

Clinically significant neurological findings will be reported as AEs.

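### Brief neurological examinations, five of the six scheduled in the Treatment Period, are listed but not summarized, so transient abnormalities not recorded as adverse events reach no by-arm table

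*SAP*

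**What the plan says.** SAP 10.4.4.2 sets the schedule: "A brief neurological examination will be performed at Visit 3 to Visit 7". The planned output is a subject listing of abnormal findings, followed by "No summaries of the brief neurological examination findings are planned". The same sentence is repeated in the SAP's amendment log (Amendment 2, Change #16); that change only narrowed the listing to abnormal findings. The section also says that clinically significant neurological findings will be reported as AEs.

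SAP 10.4.4.1 places the complete examination at "Visit 1 (entry to study), Visit 2 (Baseline), Visit 8, and at ETV in case of early termination", with later ones in the Transition and Safety Follow-Up Periods. Its output is different: "Summaries of shift from Baseline to Last Visit will be provided by treatment group", using three categories (normal; abnormal but not clinically significant; abnormal and clinically significant).

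Protocol 4.2.2 and 13.4.1 both list neurological examination findings as a safety variable. For categorical safety data, Protocol 13.4.1 says that "the number and percentage of subjects in each category will be presented by treatment group". SAP 3.9 states: "There are no changes to analyses specified in the protocol".

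**The concern.** The protocol's Introduction places central nervous system events among the most frequent TEAEs in the adult trials, and adds: "A dose relationship was seen for the most frequently reported common TEAEs, including dizziness, nausea, and diplopia". In this trial the recommended dose rises week by week in Titration: to Week 6 for the lightest weight group and to Week 4 for the other two (Protocol Table 7-1). Any effect on coordination, reflexes or strength that comes with rising dose and then fades would most likely be seen at Visits 3 to 5. Every neurological examination at those visits is a brief one.

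For subjects who complete Maintenance, the only by-arm table of examination results describes Visit 8, ten weeks after Titration ends. What is at stake is whether an imbalance in milder, passing neurological signs in children could be collected at clinic visits and yet be visible only by reading a subject listing.

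**Working it through.** The plan gives no figure to reproduce. The check is a count of examinations, then a trace of where each kind of finding is reported.

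**Count** (Protocol Table 5-1, which agrees with SAP 10.4.4.1 and 10.4.4.2):

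- Brief, Treatment Period: Visits 3, 4, 5, 6, 7 = 5.
- Complete, Treatment Period: Visit 8 (or the Early Termination Visit, ETV) = 1. Visits 1 and 2 precede the first dose.
- Share that is brief: 5 / (5 + 1) = 5/6 = 83%.
- Titration alone (Visits 3, 4, 5): 3 of 3 brief.
- If the Transition Period is added (three brief, one complete; Protocol Table 5-2): (5 + 3) / (6 + 4) = 8/10 = 80%. Placebo subjects move to lacosamide in that period, so the Treatment Period count is the relevant one for comparing arms.

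**Trace.** I take the shift table in SAP 10.4.4.1 to use complete examinations only, since 10.4.4.2 rules out any summary of the brief ones.

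| Finding on treatment | By-arm table? |
|---|---|
| Clinically significant and recorded as an AE | Yes: TEAE tables by arm, including one for Titration alone (SAP 10.2) |
| Still present at Visit 8 or at an ETV | Yes: shift table, because Last Visit is the last non-missing Treatment Period assessment (SAP 3.2.4) |
| Abnormal, not clinically significant, gone by Visit 8 or the ETV | No: listing only |
| Clinically significant, gone by then, but not recorded as an AE by the site | No: listing only |
| Seen at a brief examination, not an AE, in a subject with no complete examination after Baseline | No: listing only |

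**The AE route.** Protocol 11.9.1 tells sites: "Subsequent to Visit 1, clinically significant physical examination findings should be reported as AEs". Protocol 11.9.2, on neurological examinations, has no such sentence. The SAP supplies the rule for neurological findings, but a SAP does not instruct sites. The general AE definition in Protocol 11.1.1 does cover any unfavorable sign, so the fourth row should be uncommon.

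**Consistency within the SAP.** ECG findings are rated on the same kind of three-category scale. SAP 10.4.2 counts them by arm at every post-Baseline visit up to Visit 8 and adds shifts from Baseline. Laboratory and vital-sign abnormalities are also counted by visit (SAP 10.3 and 10.4.1). No reason is given for treating the neurological examination differently.

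**The case against.** A reader might infer that neurological abnormalities arising in Titration and resolving by Visit 8 are never compared between arms. The documents do not support that. SAP 10.4.4.2 sends clinically significant findings to AEs, and SAP 10.2 tabulates TEAEs by arm, separately for Titration and also by dose at onset. A sign troublesome enough to prompt back-titration would be expected to be recorded as an AE, and SAP 10.1 summarizes back-titration steps by arm. Subjects who stop early should have a complete examination at the ETV (Protocol 8.8), so a deficit still present then enters the shift table. All of this stands.

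It can also be said that Protocol 13.4.1 states a general presentation rule, with ECG as its example; that it says shift tables may be used; that the protocol leaves detail to the SAP; and that it promises no by-visit table for the brief examination. This is fair, and it limits the mismatch to a general rule. It does not remove it: the same section names neurological findings among the safety variables, the rule has no exception for them, and SAP 3.9 records none.

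The adult evidence also fits only in part. Diplopia is among the dose-related events, but the brief examination omits the cranial nerves (Protocol 11.9.2.2). It does include coordination.

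Finally, both examinations are described as selected assessments, and nothing in the documents shows that brief findings are recorded by domain or graded for clinical significance. That limits how detailed a table can be, and the fix allows for it.

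**Conclusion.** The point holds as a minor reporting gap. Five of six scheduled Treatment Period neurological examinations, and all three in Titration, are listed without any by-arm summary. The results left out of every by-arm table are transient abnormalities not recorded as AEs, and brief-examination results in subjects with no complete examination after Baseline. This does not match the general rule in Protocol 13.4.1 or the declaration in SAP 3.9.

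The documents give no rate for such findings, no expected difference between arms, and no number of subjects likely to miss the ETV, so the effect on the safety conclusions cannot be sized. Neurological findings are an other, not a primary, safety variable, and no efficacy analysis is touched. The verdict rests on two assumptions: that the shift table uses complete examinations only, and that sites mostly record clinically significant neurological findings as AEs, as the general AE definition requires.

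**What to change.** In SAP 10.4.4.2, replace the no-summaries sentence with:

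> The number and percentage of subjects with an abnormal neurological examination finding not present at Baseline, in the assessments common to the brief and complete examinations and by clinical significance where recorded, will be presented by treatment group at each visit (Visits 3 to 8/ETV) and for any Treatment Period visit.

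The common assessments are general neurological status, reflexes, muscle strength and coordination/cerebellar function (Protocol 11.9.2.1 and 11.9.2.2). The sponsor should first confirm how the brief examination is recorded in the eCRF; if only an overall result is held, the table should use that.

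The cost is one extra descriptive safety table from examinations already scheduled. It needs no new assessment and does not affect the primary analysis or its significance level.
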